### 17 APPENDIX E: TUMOR BIOPSIES

Instructions for Collecting, Processing and Shipping Samples

### **Archival tissues:**

Archival tissue samples should be collected from all patients enrolled in the clinical trial if they are available. Submission of paraffin embedded tissue blocks to Boston Biomedical is preferred. However, if tumor blocks are not available, 20 positively charged, unstained tissue slides at 5 micron thickness should be sent to Boston Biomedical. Archive tissue labels should be coded with the protocol number, study site number, the patient's initials and the patient number. Paraffin embedded tissue blocks or prepared tissue slides should be shipped by courier to Boston Biomedical at the address listed below.

### Fresh Tumor Biopsies:

Patients who are identified by the principal investigator as having a lesion, which could be biopsied with a minimally invasive technique, will be asked to sign an additional consent. Tumor biopsy samples should be collected at baseline and 4 hours after administration of BBI608 on Day 8 of cycle 1. Tumor biopsies will be collected for immunohistochemitry-based analysis of the target and its downstream genes and for the analysis of the effect of BBI608 on cancer stem cells. These samples will be used for research purposes only. Tumor biopsies for analysis should be collected by core biopsy or minimally invasive procedures. Tumor specimen samples should be processed sterilely into three parts: fixed, frozen, and fresh.

### Fixed Tumor Biopsies for Immunohistochemistry

The sample should be processed to yield paraffin embedded tissues by the hospital pathology department using their standard operating procedures. The samples should be labeled and coded with the protocol number, study site number, the patient's initials, the patient number and the sample collection date and time. The paraffin embedded tissue blocks should be shipped to Boston Biomedical at the address listed below.

### Fresh and Frozen Tumor Biopsy for cancer stem cell assays

Tumor biopsies for the analysis of the effect of BBI608 on cancer stem cells should be collected by core biopsy or similar minimally invasive procedures. Once the biopsy tissue is obtained, half of the biopsy tissue should be immediately and sterilely placed into CSC transport media provided by Boston Biomedical, stored and shipped at 4°C. Overnight shipment should be arranged on the same day as the biopsy is performed. A label should be affixed to all sample tubes containing with the protocol number, study site number, the patient's initials, the patient number and the sample collection date and time. The other half should be immediately snap-frozen in liquid nitrogen, and then transferred to a

polypropylene microcentrifuge cryogenic tube. The tissue sample should then be stored at ≤ -70°C until being shipped to Boston Biomedical on dry ice to the address listed below.

### **Shipping information:**

Please ship all tumor samples to the following address:

On the day that specimens are sent to Boston Biomedical, please contact Boston Biomedical by phone, fax or email to notify what is being sent and when the shipment is expected to arrive.

10. APPENDICES

1. AMENDMENTS FROM PREVIOUS VERSION(S)

Version	Date	Author(s)	Summary of Changes/Comments
Version 1.0	17SEP2018	[name]	Statistical Analysis Plan
Amendment 1	15Nov2019	[name]	Clarification of statistical methods
Amendment 2	02Mar2020	FMD	Address biostat comments
Amendment 3	09Sep2020	[name]	Address some internal comments

This is the amendment 1 of the statistical analysis plan (SAP).

2. INTRODUCTION

This statistical analysis plan (SAP) describes the statistical methods that will be used for the analyses of the clinical study report (CSR) for Boston Biomedical Protocol BBI608-224. This SAP should be read in conjunction with the study protocol and electronic case report forms (eCRFs). This version of the SAP has been developed using up to Protocol amendment 2 dated 09Oct2014.

2.1. Study Design

This is an open label, multi-center, Phase II study of napabucasin (BBI608) administered in combination with either cetuximab, or panitumumab, or capecitabine to patients with advanced colorectal cancer. The study is designed to explore the safety, tolerability, preliminary anti-tumor activity and pharmacokinetics of napabucasin when administered in combination with each one of the above regimens.

Six patients would be initially enrolled in each combination arm at a napabucasin dose level of 500 mg BID (1000 mg total daily using 50 mg capsules) before protocol amendment 2 or 480 mg twice daily (960 mg total daily dose) using 80 mg capsules after protocol amendment 2. If ≤ 1 out of 6 patients had an observable dose limiting toxicity (DLT) in the combination regimen, then that arm of the study would continue to enroll patients at 500 mg BID (1000 mg total daily) using 50 mg capsules or 480 mg BID (960 mg total daily) using 80 mg capsules following a Simon 2-stage design. If a DLT occurred in ≥ 2 of the 6 patients in a combination arm, then that arm of the study would be closed and no further patients would be enrolled. A given arm of napabucasin in combination with cetuximab, or panitumumab, or capecitabine would continue to enroll patients if no more than 1 out of 6 patients in the combination arm had an observable DLT.

The number of colorectal cancer patients enrolled would be based on a two-stage Simon design and is presented in Section 4.1 of the protocol amendment 2 [5]. If any of the three arms reach a disease control rate (DCR) of 60% or higher at the end of the Simon Stage 2 portion of the study, a one-time option to expand accrual to a total sample size of up to 50 patients may be implemented for each arm.

To evaluate the tolerability of napabucasin, patients from each arm would be assigned to one of 4 sub-cohorts (with 6 patients in each sub-cohort: IA, IB, IIA, IIB) from protocol amendment 2. The evaluation of tolerability would be done at selected centers for the study arm that was continuing patient accrual and in which a total of 50 evaluable patients had not been reached. For each

combination arm, patients assigned to sub-cohorts IA and IB would receive napabucasin at 240 mg twice daily (480 mg total daily dose) starting on Day 1 of Cycle 1. Intra-patient dose escalation of napabucasin to 480 mg twice daily (960 mg total daily dose) was allowed for patients in these cohorts as tolerated. Patients assigned to sub-cohorts IIA and IIB would receive napabucasin at 480 mg twice daily (960 mg total daily dose) starting on Day 1 of Cycle 1. In the event of toxicity, dose adjustment of napabucasin was permitted, as recommended in dose modification guidelines. Additionally, patients assigned to sub-cohorts IA and IIA would receive prophylactic anti-diarrheal treatment starting the day prior to Day 1 of Cycle 1. Patients assigned to sub-cohorts IB and IIB would receive anti-diarrheal treatment on an as-needed basis starting with development of diarrhea (ie, any occurrence greater than the patient's baseline). For each combination regimen, patients would be sequentially assigned to each of the 4 sub-cohorts in the following order until 6 patients were accrued in each of the sub-cohorts: IA, IB, IIA, and IIB. If required, up to an additional 20 patients might be assigned to selected sub-cohorts to validate the observations in the initial 6 patients.

Sub-cohort	Napabucasin Starting Dose Level	Anti-diarrheal Administration*
IA	240 mg bid (480 total daily dose) ¹	Prophylactic
IB	240 mg bid (480 total daily dose) ¹	As needed
IIA	480 mg bid (960 total daily dose) ²	Prophylactic
IIB	480 mg bid (960 total daily dose) ²	As needed

Table 1 Tolerability Analysis of Napabucasin

¹Intra-patient dose escalation of napabucasin to 480 mg po twice daily (960 mg total daily dose) is allowed as tolerated. ²In case of toxicity, dose adjustment of napabucasin is permitted.

*See protocol amendment 2 [5] section 7.1.4 for details

A study cycle would consist of 28 days of daily administration of napabucasin in combination with cetuximab or panitumumab, or capecitabine. Cycles would continue until unacceptable toxicity, disease progression (clinical or radiological) or another discontinuation criterion is met. Pharmacokinetic (PK) assessments would be performed on the first 6 patients enrolled in each combination arm. Pharmacodynamic assessments would be performed in patients with readily accessible tumor tissue through an optional tumor biopsy. Evaluation of anti-tumor activity would be performed at 8-week intervals per RECIST 1.1 while patients remain on study.

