### 10.8 Analysis and Sample size for sub-cohorts

Each sub-cohort will be analyzed for number of days of Grade II/III diarrhea and % treatment compliance achieved during the first two cycles. The % treatment compliance will be calculated as the number of capsules actually ingested over the number of capsules that should have been ingested per dose level multiplied by 100. The research questions addressed by sub-cohorts are hypothesis-generating and exploratory in nature. Initially 6 subjects will be assigned to each sub-cohort to assess the effect of intervention. Selected sub-cohorts will be extended to enroll up additional 20 patients. The decision of extending the enrollment will be based on clinical assessment without formal statistical testing. However, 20 patients will give 80% power to detect 20% difference in % treatment compliance between two arms and 57% power to detect the difference of 25% in the number of days of having Grade II/III diarrhea using two-sided Z test with pooled variance at type I error rate of 0.15. The control rates assumed are 70% for treatment compliance and 30% for diarrhea. The patients will be sequentially allocated to different sub-cohorts by the Sponsor to avoid section bias.

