8.2. Statistical Analyses

In general, all data will be summarized by arm and sub-cohort, unless otherwise specified.

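### Sub-cohort extension patients are meant to validate the first 6, but the SAP does not summarize them separately, so a pooled summary can be biased toward the results that prompted the extension

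*SAP*

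**What the plan says.** Protocol 10.8 sets the starting size: "Initially 6 subjects will be assigned to each sub-cohort to assess the effect of intervention". It then provides for the extension: "Selected sub-cohorts will be extended to enroll up additional 20 patients". SAP 2.1 gives the purpose: if required, "up to an additional 20 patients might be assigned to selected sub-cohorts to validate the observations in the initial 6 patients". Protocol 4.1 states the same purpose. On how sub-cohorts are picked, Protocol 10.8 says only this: "The decision of extending the enrollment will be based on clinical assessment without formal statistical testing". It names no endpoint, threshold or direction.

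For reporting, SAP 8.2 sets a default: "In general, all data will be summarized by arm and sub-cohort, unless otherwise specified". Neither the compliance summaries in SAP 8.2.1 nor the diarrhea-days summary in SAP 8.2.4.1 separates the first 6 patients from those added later.

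Two statements set the status of this work. Protocol 10.8 says: "The research questions addressed by sub-cohorts are hypothesis-generating and exploratory in nature". SAP 4.1 states that the study tests no hypotheses. Comparing the two starting-dose regimens and the two anti-diarrheal strategies is nevertheless a listed secondary objective (Protocol 2.2, SAP 2.1.2).

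**The concern.** Validation means checking a finding in data that did not suggest it. Here the added patients go to sub-cohorts selected after the first 6 have been observed, and under the SAP default those 6 are counted in the summary that is meant to check them. If a sub-cohort was selected because its first 6 looked unusually good or bad, part of that was probably chance, and the pooled figure carries the chance part forward. The affected outputs are diarrhea days, % compliance and dose intensity by sub-cohort. A reader of the study report could take a pooled difference as confirmed when the new patients did not show it.

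**Working it through.** **The plan's own figures.** Protocol 10.8 gives two power figures. For compliance it states: "20 patients will give 80% power to detect 20% difference in % treatment compliance between two arms". For diarrhea days its figure is 57%, at a 25-point difference. Both rest on a two-sided pooled-variance Z test at 0.15 with control rates of 70% and 30%. I read this as 20 per compared group. Power = Φ[(Δ − z·√(2p̄(1−p̄)/n)) / √((p₁(1−p₁)+p₂(1−p₂))/n)], with z = 1.4395.

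- Compliance, 70% vs 90%: Φ[(0.20 − 1.4395 × 0.1265)/0.1225] = Φ(0.146) = 55.8%. The stated 80% is not reproduced; it needs about 41 per group.
- Diarrhea, 30% vs 55%: Φ[(0.25 − 1.4395 × 0.1563)/0.1513] = Φ(0.165) = 56.6%, which matches the stated 57%. For 30% vs 5% the result is 75.1%.

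The compliance mismatch is a separate matter, and nothing below depends on it.

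**Weight of the initial 6.** When two sub-cohorts of 6 are each extended by 20, the pooled difference is (6·d₆ + 20·d₂₀)/26. If selection used only the first 6, d₂₀ averages the true difference Δ. So

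bias = (6/26) × (E[d₆ given selection] − Δ).

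The documents give no selection rule, so each rule below is an assumption.

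**Rule 1: best and worst of four extended, no true difference.**

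- Yes/no compliance at 70%: the best first 6 average 87.9% and the worst 50.7%, a gap of 37.2 points. Pooled gap = 37.2 × 6/26 = 8.6 points. A 30% diarrhea rate also gives 8.6.
- Yes/no coding implies a between-patient SD of √(0.7 × 0.3) = 45.8 points, the largest possible for a 0–100% measure with mean 70%. The actual endpoint is a per-patient percentage, and the documents give no SD. With a normal approximation the pooled gap is 2.059 × SD/√6 × 6/26, where 2.059 is the expected range of four standard normal values:

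| Assumed SD (points) | Pooled gap (points) |
|---|---|
| 10 | 1.9 |
| 20 | 3.9 |
| 30 | 5.8 |

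**Rule 2: two sub-cohorts extended only if their first-6 gap reaches a threshold (yes/no coding, exact enumeration).**

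| Threshold (patients of 6) | Gap in first 6, Δ = 0 | Pooled, Δ = 0 | Gap in first 6, Δ = 20 | Pooled, Δ = 20 |
|---|---|---|---|---|
| 1 | 27.3 | 6.3 | 31.3 | 22.6 |
| 2 | 40.0 | 9.2 | 41.9 | 25.1 |
| 3 | 54.1 | 12.5 | 54.9 | 28.1 |

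**Rule 3: selection unrelated to the first 6.** E[d₆] = Δ, so the bias is 0.

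**Rule 4: extension after a null or reversed result.** With Δ = 20 and extension only when the observed difference is 0 or less, the first 6 average −6.5. Pooled = (6 × (−6.5) + 20 × 20)/26 = 13.9 points, an understatement.

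Under every rule the 20 extension patients alone average Δ.

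**Size of the extension.** The text does not say whether 20 is per sub-cohort or in total. If 20 were shared as 10 each, the initial 6 would weigh 6/16. Rule 1 would then give 37.2 × 6/16 = about 14.0 points with yes/no coding, and 3.2, 6.3 or 9.5 points at SDs of 10, 20 or 30.

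**The case against.** The strongest reply is that the plan already limits what it claims. The sub-cohort questions are labelled exploratory, the extension is optional, the SAP specifies no between-sub-cohort estimate or test, and no sentence orders the two groups of patients to be pooled. Pooling is inferred from a general default and the absence of an exception. All of this stands, and it limits the consequence to a descriptive table. The default still governs unless something overrides it, and nothing does; the exploratory label also sits badly with a stated purpose of validation.

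A reader might infer four stronger conclusions that the documents do not support.

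- *The tolerability difference is overstated.* This needs selection on extreme first-6 results. The text gives no rule, and Rules 3 and 4 show a nil or reversed bias.
- *The benefit of a lower starting dose or of prophylaxis is exaggerated.* The 8.6 points is an unsigned best-minus-worst gap. With no true difference each sub-cohort is equally likely to be best, so the signed low-versus-high dose contrast averages essentially nil. Two of the six possible pairs (IA with IIB, IB with IIA) differ in both factors and isolate neither.
- *The false-positive rate is inflated.* Under Rule 1 with yes/no coding, the Protocol's 0.15-level test would be positive in 23.6% of trials pooled, against 15.6% in the extension patients alone. The SAP plans no such test.
- *The Protocol's 20 are the extension patients analysed alone.* The number fits, but neither document says so.

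Rule 1 also strains the plan's limits: 24 + 40 = 64 sub-cohort patients in one arm, against about 50 response-evaluable patients expected per arm (SAP 4.3). A smaller extension would fit better, but it would give the initial 6 more weight.

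**Conclusion.** The concern holds conditionally. The plan calls the extension a validation, selects sub-cohorts after the first 6 without a stated criterion, and provides no summary that separates the new patients. If selection followed the first-6 results, the pooled summary is biased toward them.

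With no true difference and 20 added to each of two sub-cohorts, the best-and-worst rule gives about 2 to 6 points for assumed SDs of 10 to 30, and 8.6 points at the yes/no extreme. Threshold rules with yes/no coding give 6.3 to 12.5 points. For scale, the Protocol's compliance target is 20 points. These figures rest on assumed selection rules and variances, so they show what could happen and are not estimates for this trial. Because the rule is unstated, a reader of the pooled table could not tell which case applies. The effect is on the description of a secondary, exploratory tolerability objective, and the primary endpoint analysis is not at issue here.

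**What to change.** Add to SAP 8.2: for any extended sub-cohort, diarrhea days, % compliance and dose intensity are reported for the extension patients alone as the validation result; the initial 6 are shown separately; the pooled figure is labelled descriptive; and the reason for extending that sub-cohort is stated. Add that a sub-cohort left at 6 offers no new patients, so a comparison against it is not an independent validation even when the other side uses extension patients only.

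The cost is one sentence or two in the SAP and one extra column per table, with no new data. The validation estimate uses up to 20 patients instead of up to 26, so its interval is wider by a factor of about √(26/20) = 1.14.

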2.2 Study Objectives

2.1.1. Primary Objectives

To determine the safety and preliminary anti-tumor activity of napabucasin when administered in combination with cetuximab, or panitumumab, or capecitabine in adult patients with advanced colorectal cancer who have failed first- and second-line treatment.

The primary endpoint is disease control rate, defined as the proportion of patients with a documented complete response, partial response and stable disease (CR + PR + SD) based on

RECIST 1.1. The secondary endpoints include progression-free survival (PFS) and overall survival (OS).

2.1.2. Secondary Objectives

The secondary objectives of this study are as follows:

- To determine the pharmacokinetic profile of napabucasin and cetuximab, or panitumumab, or capecitabine when administered in combination.
- To determine the pharmacodynamics (biomarkers) of napabucasin.
- To evaluate tolerability of two dosing regimens of napabucasin by comparing administration of napabucasin at a 240 mg twice daily starting dose and escalating to 480 mg twice daily after Cycle 1 versus administration of napabucasin at a 480 mg twice daily starting dose with dose adjustment permitted.
- To evaluate tolerability of napabucasin by comparing prophylactic administration of anti-diarrheal medication versus as-needed administration of anti-diarrheal medication. The tolerability will be assessed using the adverse event profile and achieved dose intensity.

3. ENDPOINTS AND COVARIATES: DEFINITIONS AND CONVENTIONS

3.1. Primary Endpoint(s)

• Disease Control Rate (DCR), defined in section 2.1.1

3.2. Secondary Endpoints

- PK parameters of napabucasin administered in combination with cetuximab, or panitumumab, or capecitabine.
- PK parameters of capecitabine and metabolite (5-FU).
- Pharmacodynamics parameters (or biomarkers) of napabucasin administered in combination with cetuximab, or panitumumab, or capecitabine. Response (increase or decrease) of several biomarkers of napabucasin from biopsied tumors following napabucasin administration will be examined in patients with accessible tumors who consent to an optional biopsy.
- Objective Response Rate (ORR)

ORR is defined as the percentage of patients with a best overall response (BOR) of complete response (CR) or partial response (PR). The categorizations of response (CR, PR, SD, PD, and NE) and the derivations of BOR is provided in Appendix 1.1 and 1.2.

• Progression Free Survival (PFS) and Overall Survival (OS)

PFS is defined as the time from the date of first treatment (or date of enrollment in sensitivity analysis) to the date of first documentation of progressive disease (PD) or death due to any cause, whichever occurs first.

OS is defined as the time from the date of treatment (or date of enrollment in sensitivity analysis) to the date of death. Patients without documentation of death at the time of analysis will be censored at the date last known to be alive.

• Dose Limiting Toxicities (DLTs): For definition of DLT, see Section 4.5 of the protocol amendment 2 [5].

3.3. Other Endpoints

- Adverse Events (AEs) characterized by type, frequency, severity (graded by National Cancer Institute Common Terminology Criteria for Adverse Events [NCI CTCAE] version 4.0], timing, seriousness, and relationship to study therapy
- Laboratory abnormalities characterized by type, frequency, severity (graded by NCI CTCAE version 4.0), and timing.

3.4. Covariates

Demographic and baseline disease characteristics may be considered as covariates in population PK, PK/PD (biomarker), and anti-tumor efficacy exploratory analyses.

4. HYPOTHESES AND DECISION RULES

4.1. Statistical Hypotheses

There is no hypothesis testing in this study.

4.2. Statistical Decision Rules

4.2.1. DLT Decision Rule

DLT decisions are based on the observed number of patients with DLT at 480 mg BID napabucasin.

Number of Patients with DLT at 480 mg bid	DLT Decision Rule	
≤ 1 out of 6	Continue patient enrollment in combination arm	
\geq 2 out of 6	Close combination arm of the study	

4.2.2. Simon's Design Decision Rule

The Simon's design decision rule is described in Section 4.1 of protocol amendment 2 [5], but the study was not conducted following the Simon two-stage design and no Simon's design decision rule was applied.

4.3. Sample Size Justification

The sample size for this study was determined by clinical rather than statistical considerations. The exact number of patients estimated for this trial is dependent on the number of patient cohorts investigated based on the toxicity encountered. It is expected that up to a total of approximately 50 response evaluable patients will be enrolled in each combination arm during the study. Patients who have received at least one cycle of study treatment unless discontinued due to death or PD and have had at least one disease assessment following the initiation of therapy will be considered evaluable for response.

5. INTERIM ANALYSES

No formal interim analyses are planned for this study.

6. ANALYSIS SETS

6.1. Full Analysis Set

The full analysis set (FAS) includes all enrolled patients.

6.2. Safety Analysis Set

The safety population is defined as all patients who receive at least 1 dose of any study drug. The safety population will be used for all safety-related analyses such as AEs, concomitant medications, laboratory tests, and vital signs.

